2. We will assess LA GLS using an automated measurement tool called AutoSTRAIN by TOMTEC-ARENA (<https://www.tomtec.de/products/application-finder/autostain/>). The historic echocardiograms from patients who meet the study inclusion criteria will be uploaded into this software, which was newly acquired by the PBMC Cardiology Department. MaineHealth Information Services are currently working with study staff to assure appropriate security compliance within the network. LA GLS has not been routinely collected previously from echocardiograms performed at PBMC because of a lack of such technology.
3. We will use statistical methods to describe the relationship between LA GLS and maintenance of sinus rhythm six months post-cardioversion among the AF patients included in this study.

2 Study Design

This study has both retrospective and prospective components. There is an enrollment goal of 500 subjects.

For the retrospective portion, patients will be identified for inclusion in the study based on a previous documented diagnosis of AF, have a documented echocardiogram done prior to the cardioversion with images available in the MaineHealth electronic medical record (EMR), and have undergone electrical cardioversion at a MaineHealth institution.

For the prospective portion of the study, patients will be identified by the PBMC echocardiographic technicians prior to elective cardioversion. The patient will be consented prior to the administration of any sedative. If the patient consents, they will be followed for 6 months after the procedure via the EMR only. The prospective portion of the study will only be conducted at PBMC and not at other MaineHealth institutions due to the lack of staffing capacity at the investigative site.

3 Subject Selection and Withdrawal (if applicable)

3.1 *Inclusion Criteria*

- Patients identified at any MaineHealth site with a documented diagnosis of AF (at any point in time prior to the cardioversion) and who have undergone any cardioversion.
- The patient would also need to have had an echocardiogram within six months pre-cardioversion (performed for any reason) with a well visualized atrial roof in order to perform the measurements accurately using the TOMTEC-ARENA software.
- For the prospective portion of the study – must be willing to provide informed consent

3.2 *Exclusion Criteria*

- Patients with a mitral regurgitation greater than moderate (effective regurgitant orifice $\geq .2 \text{ mm}^2$)

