3.3 Subject Recruitment and Screening

Subjects will be identified using a retrospective chart review within EPIC, between January 1, 2017, through June 30, 2021. These patients will have a diagnosis of atrial fibrillation, a documented echocardiogram, and cardioversion therapy. The study staff will review the medical records in EPIC of these patients and screen for the other inclusion/exclusion elements described above.

For the prospective portion of the study, potential subjects will be identified by the PBMC echocardiographic technicians prior to cardioversion. Either one of the echocardiographic technicians or one of the PBMC Clinical Research coordinators will explain the study to the patient and obtain informed consent.

4 Storage of Study Materials

Study data will be entered into and maintained in a web-based, HIPAA-compliant REDCap database which has a password protected login and only accessed by appointed study staff. These staff include a cardiac sonographer, the clinical research manager at PBMC, and the Rural Research Navigator at the Center for Outcomes Research and Evaluation (CORE), each of which will have full read/write access to the database. Information about study subjects will be kept confidential and managed according to the requirements of the Health Insurance Portability and Accountability Act of 1996 (HIPAA). Once the dataset is complete, all identifiers (medical record numbers and dates of health events or services) will be deleted and subjects will be identified by a unique study ID#, assigned by REDCap. Only de-identified data will be downloaded for analysis.

5 Data collection and management

The study staff- one cardiac sonographer, the clinical research manager at PBMC, and the Rural Research Navigator at CORE- will request an extract of EPIC patient data from Enterprise Reporting based on the inclusion criteria of atrial fibrillation, a documented echocardiogram, and electrical cardioversion therapy, including these codes:

	ICD-9	ICD-10	CPT
Atrial fibrillation	427.31		
Atrial flutter	427.32		
Paroxysmal atrial fibrillation		I48.0	
Persistent atrial fibrillation		I48.1	
Chronic atrial fibrillation		I48.2	
Typical atrial flutter		I48.3	
Atypical atrial flutter		I48.4	
Unspecified atrial fibrillation		I48.91	
Unspecified atrial flutter		I48.92	
Transthoracic stress echo, complete			93350
Transthoracic stress echo, complete w cont EKG			93351
Transthoracic echo cardiac anomalies			93303

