Transthoracic echo cardiac anomalies, limited			93304
Transthoracic echo complete w color & spectral			93306
Transthoracic echo complete wo color & spectral			93307
Transthoracic echo limited			93308
Cardioversion (nonemergency), elective, electrical			92960

The study staff will review the medical records in EPIC of these patients and screen for the other inclusion/exclusion elements described above. Patients who meet this criteria will be included in the study and have their medical record number documented in REDCap (a secure, HIPAA compliant, web-based database portal). If these patients are living and scheduled for a follow-up visit at PBMC, they will be consented to be included in the study by one of the study staff. If they do not consent to be included in the study, their information will be deleted from the REDCap database. If they are no longer living or have already had a follow-up visit at the time of the study start date, consent will not be obtained. For those included in the study, medical record numbers, along with demographics, BMI, date of atrial fibrillation diagnosis, antiarrhythmic medications, date(s) of echocardiogram(s) and cardioversion(s) performed, and whether sinus rhythm was maintained at least six months post-cardioversion either by electrocardiogram (ECG), holter monitor, telemetry monitoring or cardiologist dictated note. These patients' echocardiography images will be obtained pre-cardioversion from EPIC and uploaded to the TOMTEC software in order to obtain the LA GLS measurements (as continuous data).

GLS is derived via validated methods [10] using a calculation of:
$$\epsilon = \frac{L1 - L0}{L0} \times 100\%$$

It has proven to be clinically reproducible as reported in a prior study [11]. While the TOMTEC vendor does not provide normal range values for clinical interpretation, the literature provides GLS measurement data for comparison among nine different software vendors, including TOMTEC [12].

In short, we will:

1. Identify patients at with AF, who obtained an echocardiogram and cardioversion.
2. Consent patients who meet the inclusion criteria who are living and who will be returning for their six month follow-up visit.
3. For patients who have consented or who are deceased, or who have already presented for their six month follow-up visit by the time the study has started, the following information will be collected:
 - a. Dates of echocardiogram(s) and cardioversion(s) performed

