 - b. Determine maintenance of sinus rhythm at least six months post cardioversion
 - c. Medical Record Number
 - a. Sex
 - b. Age
 - c. Race/ethnicity
 - d. Weight
 - e. Date of first atrial fibrillation diagnosis
 - f. Number of AF recurrence visits
 - g. Antiarrhythmic medications
 - h. Smoking status
 - i. Number of shocks at cardioversion
 - j. Post-ablation procedure
 - k. Hypertension
 - l. Diabetes
 - m. COPD
 - n. Obstructive sleep apnea
 - o. Renal impairment
 - p. Hyperthyroidism
 - q. Coronary artery disease
 - r. Congestive heart failure
 - s. Left systolic dysfunction
 - t. Left diastolic dysfunction
 - u. Left ventricular hypertrophy
 - v. Valvular heart disease
4. Also within this population, obtain echocardiographic features/ measurements:
 - a. GLS of LA of 4 chamber
 - b. GLS of LA of 2 chamber

c. LAVI (Left atrial volume index)

Aside from the echocardiographic features, all of the above data elements will be in EPIC and extracted into a REDCap database. The echocardiographic features will be obtained by the two cardiac sonographers utilizing the TOMTEC software, and will document these in REDCap. Patient medical record numbers and dates of health events or services (date of cardioversion, date of atrial fibrillation diagnosis, and date of echocardiogram) will be removed from the database after the six month follow-up visit and documentation of normal sinus rhythm occurs. Time lapsed between echocardiogram(s) and duration of atrial fibrillation will be calculated fields created in REDCap based on dates of echocardiogram(s) and date of first atrial fibrillation diagnosis, respectively. Once the time lapsed variables have been created, the date variables will be removed from the database.

Subject information will be kept in the PBMC Echocardiographic lab and the PBMC Clinical Research office, which are both locked when unattended. Information entered into a REDCap database which is password protected. Information about study subjects will be kept confidential and managed according to the requirements of the Health Insurance Portability and Accountability Act of 1996 (HIPAA).

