Subject information will be kept in the PBMC Echocardiographic lab and the PBMC Clinical Research office, which are both locked when unattended. Information entered into a REDCap database which is password protected. Information about study subjects will be kept confidential and managed according to the requirements of the Health Insurance Portability and Accountability Act of 1996 (HIPAA).

- Protected health information (PHI), which will be collected from subject charts in this study, include demographics (age, sex), echocardiogram results, and maintenance of normal sinus rhythm. Patient medical record numbers will be used for linking the prospective information related to maintenance of normal sinus rhythm, and will be deleted after this information is documented in REDCap.
- Time lapsed between echocardiogram(s) and duration of atrial fibrillation will be calculated fields created in REDCap based on dates of echocardiogram(s) and date of first atrial fibrillation diagnosis, respectively. Once the time lapsed variables have been created, the date variables will be removed from the database.
- Only the cardiac sonographers and the PBMC clinical research nurse manager will have access to this information.

8 Potential problems

The number of patients included (since early 2017) could be too small to meet our target number of 500.

References

1. *Atrial Fibrillation Fact Sheet*. 2017 [cited 2017 October 23, 2017]; Available from: https://www.cdc.gov/dhdsp/data_statistics/fact_sheets/fs_atrial_fibrillation.htm
2. Tsang, T.S., et al., *Left atrial volume: important risk marker of incident atrial fibrillation in 1655 older men and women*. Mayo Clin Proc, 2001. **76**(5): p. 467-75.
3. Mozaffarian, D., et al., *Heart disease and stroke statistics--2015 update: a report from the American Heart Association*. Circulation, 2015. **131**(4): p. e29-322.
4. Gronberg, T., et al., *Can we predict the failure of electrical cardioversion of acute atrial fibrillation? The FinCV study*. Pacing Clin Electrophysiol, 2015. **38**(3): p. 368-75.
5. Berry, C., et al., *Electrical cardioversion for atrial fibrillation: outcomes in "real-life" clinical practice*. Int J Cardiol, 2001. **81**(1): p. 29-35.
6. Ecker, V., et al., *A review of factors associated with maintenance of sinus rhythm after elective electrical cardioversion for atrial fibrillation*. Clin Cardiol, 2018. **41**(6): p. 862-870.

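### The mitral regurgitation exclusion pairs a verbal grade with an orifice area that, as printed, is implausibly small, and no rule says which governs; check the unit against the source first

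*Combined protocol and SAP*

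**What the plan says.** Section 3.2 lists as an exclusion "Patients with a mitral regurgitation greater than moderate (effective regurgitant orifice $\geq .2 \text{ mm}^2". The verbal grade comes first and the orifice area follows in parentheses as its apparent equivalent. No other orifice area appears in the documents.

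The bullet applies to both parts of the study. The only line in sections 3.1 and 3.2 specific to one part is the prospective consent line ("must be willing to provide informed consent").

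For the retrospective part, section 3.3 says: "The study staff will review the medical records in EPIC of these patients and screen for the other inclusion/exclusion elements described above". Section 5 repeats this and identifies the staff as "The study staff- one cardiac sonographer, the clinical research manager at PBMC, and the Rural Research Navigator at CORE". It then says: "Patients who meet this criteria will be included in the study and have their medical record number documented in REDCap".

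In the section 5 data list, the nearest clinical item is "Valvular heart disease". The echocardiographic items are the two left atrial strain views and "LAVI (Left atrial volume index)". Neither regurgitation grade nor orifice area is listed.

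**The concern.** An eligibility bullet should lead any two readers of the same chart to the same decision. This one offers two tests. One is a grade, with exclusion only above moderate. The other is an area, with exclusion at or above a value that, as printed, describes a pinhole. A screener who relies on the grade and one who relies on the number could disagree about a patient whose chart gives both.

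Only one of the three named screening roles is a cardiac sonographer, so consistency depends on the written rule. Inconsistency would also be hard to see afterwards, because neither grade nor area is a listed data item. Any avoidable exclusions would work against the one difficulty the plan names for itself in section 8: "The number of patients included (since early 2017) could be too small to meet our target number of 500".

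**Working it through.** **Inputs.** The grade (above moderate) and the value (at least .2 mm²) come from section 3.2. The plan derives the value from nothing else, so there is no calculation of its own to reproduce. The checks below ask what the printed value means physically.

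**1. Unit conversion.** 1 cm² = 100 mm², so 0.2 mm² = 0.2 / 100 = 0.002 cm².

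**2. Equivalent circular opening.** d = 2 × √(A/π) = 2 × √(0.2/π) = 0.505 mm, or about half a millimetre.

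**3. Leak per beat.** Volume = area × velocity-time integral of the jet. The documents give no integral; 80 to 200 cm is assumed here.
- 0.002 cm² × 80 cm = 0.16 mL
- 0.002 cm² × 200 cm = 0.40 mL

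**4. Share of charted areas at or above 0.2 mm².** The documents give no distribution. For illustration only, assume lognormal areas with median m from 1 to 20 mm² and log-SD s of 0.7 or 1.0. The share is 1 − Φ((ln 0.2 − ln m)/s).

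| m (mm²) | s = 0.7 | s = 1.0 |
|---|---|---|
| 1 | 0.989 | 0.946 |
| 5 | 1.000 | 0.999 |
| 10 | 1.000 | 1.000 |
| 20 | 1.000 | 1.000 |

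Under these assumptions the printed figure catches about 95% to 100% of patients who have an area on the chart. It catches nobody for whom only a verbal grade is charted.

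**5. Sensitivity to the unit.** If the unit were cm² (an assumption used only to show what one letter does, not a proposal), 0.2 cm² = 20 mm² and d = 2 × √(20/π) = 5.05 mm. The area changes by 20 / 0.2 = 100-fold. The plausibility finding therefore rests on one character of machine-read text, with no second occurrence to compare.

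**6. The words beside the number.** The grade is a strict bound (above moderate) and the area an inclusive one (at or above the value). Nothing in the documents maps one to the other, cites a source for the cutoff, says which takes precedence, or says what to do when no area is charted.

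**The case against.** The strongest reply is that this may not be the sponsor's error at all. The text was read from a PDF, and if the source prints a different unit, steps 1 to 4 fall away. The documents alone could not then show that the grade and the number disagree. This stands, and it is why the source check comes first. A missing precedence rule would remain, but it would matter only if the two tests diverge.

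Second, a reader might infer that the number necessarily excludes more patients than the words, with everyone above moderate meeting both tests. The documents do not support that, because it needs an area-to-grade scale and they contain none. What can be said is conditional: if some patients at or below moderate have a charted area of at least 0.2 mm², a literal reader would exclude patients whom the words keep.

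Third, staff may simply apply the grade, which leads the sentence, and nothing shows that areas are routinely charted. This also stands: the practical effect may be nil. For the same reason, a reader should not infer any particular shortfall against the target of 500. Any assumed share of extra exclusions would have no source in the documents.

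Nor should a reader infer bias in the left atrial strain comparison of section 6. Nothing in the documents shows that the extra exclusions, if any, would be related to both strain and rhythm outcome.

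**Conclusion.** The point holds in limited form. As supplied, an operative eligibility threshold equates above-moderate regurgitation with an opening about 0.50 mm across, leaking 0.16 to 0.40 mL per beat at the assumed integral. That is implausible on its face. Applied literally, it could exclude practically any patient with a charted orifice area. With no scale, source or precedence rule, screeners could differ on the same chart.

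The conclusion assumes that the unit was read correctly from the PDF. The judgement of implausibility also takes it that above-moderate regurgitation leaks more than a fraction of a millilitre per beat. The number of patients affected cannot be estimated and may be zero. This should be corrected because it is an eligibility rule and cheap to repair, not because harm to the results has been shown.

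**What to change.** 1. Compare the bullet, above all its unit, with the source document. If the supplied text misread it, the plausibility point is withdrawn.
2. If it is as printed, the investigator should reconcile the verbal grade, inequality, value and unit into one consistent criterion, and state what applies when no orifice area is charted. The same criterion should be used in the retrospective and prospective parts. No threshold, unit or grade is prescribed here.
3. Ask the screening staff which test they applied. If anyone was excluded on the literal figure, re-check those patients.

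The text change is one line. Step 3 may cost more: section 5 describes recording record numbers in REDCap for patients who meet the criteria, and the plan describes no log of exclusions. Finding the affected patients could therefore mean re-screening part of the EPIC extract. If staff used only the verbal grade, step 3 ends with their answer.

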3.3 Subject Recruitment and Screening

Subjects will be identified using a retrospective chart review within EPIC, between January 1, 2017, through June 30, 2021. These patients will have a diagnosis of atrial fibrillation, a documented echocardiogram, and cardioversion therapy. The study staff will review the medical records in EPIC of these patients and screen for the other inclusion/exclusion elements described above.

For the prospective portion of the study, potential subjects will be identified by the PBMC echocardiographic technicians prior to cardioversion. Either one of the echocardiographic technicians or one of the PBMC Clinical Research coordinators will explain the study to the patient and obtain informed consent.

4 Storage of Study Materials

Study data will be entered into and maintained in a web-based, HIPAA-compliant REDCap database which has a password protected login and only accessed by appointed study staff. These staff include a cardiac sonographer, the clinical research manager at PBMC, and the Rural Research Navigator at the Center for Outcomes Research and Evaluation (CORE), each of which will have full read/write access to the database. Information about study subjects will be kept confidential and managed according to the requirements of the Health Insurance Portability and Accountability Act of 1996 (HIPAA). Once the dataset is complete, all identifiers (medical record numbers and dates of health events or services) will be deleted and subjects will be identified by a unique study ID#, assigned by REDCap. Only de-identified data will be downloaded for analysis.

5 Data collection and management

The study staff- one cardiac sonographer, the clinical research manager at PBMC, and the Rural Research Navigator at CORE- will request an extract of EPIC patient data from Enterprise Reporting based on the inclusion criteria of atrial fibrillation, a documented echocardiogram, and electrical cardioversion therapy, including these codes:

	ICD-9	ICD-10	CPT
Atrial fibrillation	427.31		
Atrial flutter	427.32		
Paroxysmal atrial fibrillation		I48.0	
Persistent atrial fibrillation		I48.1	
Chronic atrial fibrillation		I48.2	
Typical atrial flutter		I48.3	
Atypical atrial flutter		I48.4	
Unspecified atrial fibrillation		I48.91	
Unspecified atrial flutter		I48.92	
Transthoracic stress echo, complete			93350
Transthoracic stress echo, complete w cont EKG			93351
Transthoracic echo cardiac anomalies			93303
Transthoracic echo cardiac anomalies, limited			93304
Transthoracic echo complete w color & spectral			93306
Transthoracic echo complete wo color & spectral			93307
Transthoracic echo limited			93308
Cardioversion (nonemergency), elective, electrical			92960

The study staff will review the medical records in EPIC of these patients and screen for the other inclusion/exclusion elements described above. Patients who meet this criteria will be included in the study and have their medical record number documented in REDCap (a secure, HIPAA compliant, web-based database portal). If these patients are living and scheduled for a follow-up visit at PBMC, they will be consented to be included in the study by one of the study staff. If they do not consent to be included in the study, their information will be deleted from the REDCap database. If they are no longer living or have already had a follow-up visit at the time of the study start date, consent will not be obtained. For those included in the study, medical record numbers, along with demographics, BMI, date of atrial fibrillation diagnosis, antiarrhythmic medications, date(s) of echocardiogram(s) and cardioversion(s) performed, and whether sinus rhythm was maintained at least six months post-cardioversion either by electrocardiogram (ECG), holter monitor, telemetry monitoring or cardiologist dictated note. These patients' echocardiography images will be obtained pre-cardioversion from EPIC and uploaded to the TOMTEC software in order to obtain the LA GLS measurements (as continuous data).

GLS is derived via validated methods [10] using a calculation of:
$$\epsilon = \frac{L1 - L0}{L0} \times 100\%$$

It has proven to be clinically reproducible as reported in a prior study [11]. While the TOMTEC vendor does not provide normal range values for clinical interpretation, the literature provides GLS measurement data for comparison among nine different software vendors, including TOMTEC [12].

In short, we will:

1. Identify patients at with AF, who obtained an echocardiogram and cardioversion.
2. Consent patients who meet the inclusion criteria who are living and who will be returning for their six month follow-up visit.
3. For patients who have consented or who are deceased, or who have already presented for their six month follow-up visit by the time the study has started, the following information will be collected:
 - a. Dates of echocardiogram(s) and cardioversion(s) performed
 - b. Determine maintenance of sinus rhythm at least six months post cardioversion
 - c. Medical Record Number
 - a. Sex
 - b. Age
 - c. Race/ethnicity
 - d. Weight
 - e. Date of first atrial fibrillation diagnosis
 - f. Number of AF recurrence visits
 - g. Antiarrhythmic medications
 - h. Smoking status
 - i. Number of shocks at cardioversion
 - j. Post-ablation procedure
 - k. Hypertension
 - l. Diabetes
 - m. COPD
 - n. Obstructive sleep apnea
 - o. Renal impairment
 - p. Hyperthyroidism
 - q. Coronary artery disease
 - r. Congestive heart failure
 - s. Left systolic dysfunction
 - t. Left diastolic dysfunction
 - u. Left ventricular hypertrophy
 - v. Valvular heart disease
4. Also within this population, obtain echocardiographic features/ measurements:
 - a. GLS of LA of 4 chamber
 - b. GLS of LA of 2 chamber

c. LAVI (Left atrial volume index)

Aside from the echocardiographic features, all of the above data elements will be in EPIC and extracted into a REDCap database. The echocardiographic features will be obtained by the two cardiac sonographers utilizing the TOMTEC software, and will document these in REDCap. Patient medical record numbers and dates of health events or services (date of cardioversion, date of atrial fibrillation diagnosis, and date of echocardiogram) will be removed from the database after the six month follow-up visit and documentation of normal sinus rhythm occurs. Time lapsed between echocardiogram(s) and duration of atrial fibrillation will be calculated fields created in REDCap based on dates of echocardiogram(s) and date of first atrial fibrillation diagnosis, respectively. Once the time lapsed variables have been created, the date variables will be removed from the database.

Subject information will be kept in the PBMC Echocardiographic lab and the PBMC Clinical Research office, which are both locked when unattended. Information entered into a REDCap database which is password protected. Information about study subjects will be kept confidential and managed according to the requirements of the Health Insurance Portability and Accountability Act of 1996 (HIPAA).

- Protected health information (PHI), which will be collected from subject charts in this study, include demographics (age, sex), echocardiogram results, and maintenance of normal sinus rhythm. Patient medical record numbers will be used for linking the prospective information related to maintenance of normal sinus rhythm, and will be deleted after this information is documented in REDCap.
- Time lapsed between echocardiogram(s) and duration of atrial fibrillation will be calculated fields created in REDCap based on dates of echocardiogram(s) and date of first atrial fibrillation diagnosis, respectively. Once the time lapsed variables have been created, the date variables will be removed from the database.
- Only the cardiac sonographers and the PBMC clinical research nurse manager will have access to this information.

6 Analysis Plan

The duration of AF will be calculated for each patient utilizing the date of first AF diagnosis and the date(s) of cardioversion(s). Descriptive statistics will be used to summarize the demographic and clinical characteristics of patients included in the study, with continuous variables presented as a mean + standard deviation and categorical variables as frequencies/percentages of the total.

A t-test will be utilized to compare the mean LA GLS among patients documented to have maintenance of sinus rhythm at 6 months to those who have not.

A binary logistic regression model will be developed in order to model any predictive factors (independent variable: echocardiographic features/measurements) among those who have maintained sinus rhythm vs. those who have not (dependent variable: sinus rhythm yes/no) within six months of cardioversion. Criteria for selecting other variables listed above for entry into the logistic regression model will be based on univariate analysis of each variable. Variables determined to have a significant univariate test with a p-value cutoff of 0.05 will be included in the model. Variables deemed not significant will be assessed for confounding by observing parameter estimate changes >10% when variables are excluded from the full model. Analyses will be performed using SAS by the Rural Research Navigator at the Center for Outcomes Research and Evaluation at the Maine Medical Center Research Institute.

7 Confidentiality

Subject information will be kept in the PBMC Echocardiographic lab and the PBMC Clinical Research office, which are both locked when unattended. Information entered into a REDCap database which is password protected. Information about study subjects will be kept confidential and managed according to the requirements of the Health Insurance Portability and Accountability Act of 1996 (HIPAA).

- Protected health information (PHI), which will be collected from subject charts in this study, include demographics (age, sex), echocardiogram results, and maintenance of normal sinus rhythm. Patient medical record numbers will be used for linking the prospective information related to maintenance of normal sinus rhythm, and will be deleted after this information is documented in REDCap.
- Time lapsed between echocardiogram(s) and duration of atrial fibrillation will be calculated fields created in REDCap based on dates of echocardiogram(s) and date of first atrial fibrillation diagnosis, respectively. Once the time lapsed variables have been created, the date variables will be removed from the database.
- Only the cardiac sonographers and the PBMC clinical research nurse manager will have access to this information.

8 Potential problems

The number of patients included (since early 2017) could be too small to meet our target number of 500.

References

1. *Atrial Fibrillation Fact Sheet*. 2017 [cited 2017 October 23, 2017]; Available from: https://www.cdc.gov/dhdsp/data_statistics/fact_sheets/fs_atrial_fibrillation.htm
2. Tsang, T.S., et al., *Left atrial volume: important risk marker of incident atrial fibrillation in 1655 older men and women*. Mayo Clin Proc, 2001. **76**(5): p. 467-75.
3. Mozaffarian, D., et al., *Heart disease and stroke statistics--2015 update: a report from the American Heart Association*. Circulation, 2015. **131**(4): p. e29-322.
4. Gronberg, T., et al., *Can we predict the failure of electrical cardioversion of acute atrial fibrillation? The FinCV study*. Pacing Clin Electrophysiol, 2015. **38**(3): p. 368-75.
5. Berry, C., et al., *Electrical cardioversion for atrial fibrillation: outcomes in "real-life" clinical practice*. Int J Cardiol, 2001. **81**(1): p. 29-35.
6. Ecker, V., et al., *A review of factors associated with maintenance of sinus rhythm after elective electrical cardioversion for atrial fibrillation*. Clin Cardiol, 2018. **41**(6): p. 862-870.
